8.2.4 Subject Stopping Guidelines

This guideline is to be used to indicate boundaries requiring discussion by the Data and Safety Monitoring Board (DSMB) and is designed to assist the independent DSMB in overseeing the study. The DSMB may also request additional interim analyses and develop other criteria including provision for monitoring of potential late effects to determine when to intervene in the enrollment or treatment of subjects in the study. The first more conservative stopping guideline is to monitor subjects for unexpected SAEs where there is a reasonable possibility that the study product or administration procedure caused the event within 30 days of administration including subject death, grade 3 myocardial infarction, or grade 3 hemodynamically unstable ventricular tachycardia. Study accrual and further treatment of subjects will be put on hold if any subjects experience one of these events. The DSMB will be notified within 24 hours of the occurrence of these events and will be convened within 3 business days to review the event and study.

The following are subject stopping guidelines:

1. Any subject who develops persistent (that is, still existing more than 3 hours after the end of IP infusion) cardiorespiratory signs or symptoms (for example, shortness of breath, tachypnea, tachycardia, hypotension, or palpitations) will continue with all scheduled follow-up if such follow-up is considered safe in the opinion of the Investigator. A subject may still be able to receive additional infusions, based on the investigator's judgement.
2. Any subject whose infusion is stopped due to cardiorespiratory distress will not receive further IP infusions until it is considered safe in the opinion of the Investigator, but subjects will continue with all scheduled follow-up if such follow-up is considered safe. A subject may still be able to receive additional infusions, based on the investigator's judgement.
3. The proportion of subjects experiencing TE-SAE as defined in Section 2.2.1 will be monitored within 30 days of infusion. This guideline is designed to assist the independent DSMB in overseeing the study and indicate boundaries needing discussion by the DSMB. The DSMB may also request additional interim analyses and develop other criteria including provision for monitoring of potential late effects to determine when to intervene in the enrollment or treatment of subjects in the study.

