8.2.5 Subject observation and discontinuation after IP administration

The IP administration guidelines in **Appendix 1** list the study requirements for subject observation and discharge after IP administration.

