10. Return the blinded IP infusion bag to the cell-processing technician.

Procedures post-infusion:

1. Vital signs will be monitored at 15 minutes, 30 minutes, 1 hour, and 2 hours post IP infusion
2. The subject will be monitored for a minimum of 2 hours post IP infusion with continuous pulse oximetry
3. If the O₂ saturation decreases to < 90% over a continual period of 3 – 5 minutes then supplemental oxygen may be added or increased during the two-three hours post-infusion observation period.
4. If at the end of the 2 hour observation period, if a subject's O₂ saturation stays below 90% then the subject will be provided additional oxygen to maintain a saturation of >90% at room air up to 4 hours post infusion.
5. After the minimum two hour observation period, the subject will be continuously monitored and discharged, if no complaints are experienced, such as shortness of breath or other objective signs of cardiorespiratory compromise.
6. Subjects not meeting criteria for discharge will be assessed by the Investigator during the observation period to further determine hospitalization otherwise not specified in the protocol.

Subject Stopping Guidelines:

1. Any subject who develops persistent (that is, still existing more than 3 hours after the end of IP infusion) cardiorespiratory signs or symptoms including hypoxemia (defined per oxygenation criteria of 93% on room air at rest, or shortness of breath, tachypnea, tachycardia, hypotension, or palpitations) will continue with all scheduled follow-up if such follow-up is considered safe in the opinion of the Investigator. The infusion will be stopped if the oxygen saturation does not return to >93% within 3 minutes of initiating supplemental oxygen or if the subject requires greater than 2L/min supplemental oxygen to achieve the required saturation of >93%. If a subject requires the addition of oxygen, it will be continued for 4 hours after the completion of the infusion. At that time, oxygen will be weaned off to maintain a saturation >93% on room air.
2. Any subject whose infusion is stopped due to cardiorespiratory distress will receive no further IP infusions but will continue with all scheduled follow-up if such follow-up is considered safe in the opinion of the Investigator.

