3. Any subject who develops any sign or symptom that, at the discretion of the Investigator, warrants the discontinuation of infusion will receive no further IP infusions but will continue with all scheduled follow-up if such follow-up is considered safe in the opinion of the Investigator.
4. Infusion of the IP may be stopped if there is an adverse event that the Investigator believes is related to the IP or if there is an issue with the IP infusion.

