The evidence supports the conclusion that it is feasible to dose subjects in this study based on a standard dose of hMSCs rather than per kilogram of body weight. The total cell number corresponds to a range of 1.3 - 4.4 x 10^6 hMSCs per kg per infusion for subjects with 45 to 150kg body weight, the weight range for this study.

Therefore, results from previous trials support the rationale on the safety and potential efficacy of a second infusion of the selected maximum dose of 100 x 10^6 allo-hMSCs.

A.7 Administration Rate

Prior clinical trials have used rates up to 30x 10^6 hMSC/min where no infusion related toxicity was observed.

In the proposed study addendum, the cell dose to be delivered is 1 x 10^8 (100 million), in the following total volume:

- 40ml for 100 million dose (5 million hMSC/min)

Cells are placed in an 80ml bag and will be delivered at a rate of 2ml/min, and delivered at a maximum rate of 16x 10^6 hMSC/minute and will last approximately:

- 40 minutes for delivery of 40ml of 100 million dose in an 80 ml bag

A.8 Data and Safety Monitoring Board (DSMB)

DSMB will continue to provide the same oversight as noted in Section 9.4 of the Main protocol.

A.9 Concomitant Treatments, Procedures, and Nondrug Therapies

Refer to section 4.3 of the main study protocol

A.10 Infusion Monitoring Guidelines

Refer to section 6.4.1 and Appendix 1 of the main protocol.

A.11 Adverse Events and Serious Adverse Events

Refer to section 8.9 through 8.15 of the main study protocol.

A.12 Stopping Guidelines

Refer to section 8.2.4 of the main study protocol for further stopping guidelines.

A.13 Payments to Subjects and Donors in the Follow-on Phase

Subjects will be reimbursed \$25 at the end of each follow-up visit (Month 1 – Month 6 for a total remuneration of \$75. These disbursements are meant to cover the time required to complete these study visits and all necessary travel and parking expenses.

Normal donors for generation of allo-MSC will be reimbursed \$500 at the end of BM aspiration. This payment will compensate donors for lost time, parking, and travel expenses.

A.14 Study Procedures for Pilot Phase Optional Second Infusion

Table A1: Time and Events Table for Optional Pilot Phase Second Infusion Schedule

Visit Schedule for Second Infusion	Screening ± 6 Months	Baseline (-4 weeks)	Day 1	Month 1 (Day 30) (+/- 2 weeks)	Month 3 (Day 90) (+/- 30 days)	Month 6 (Day 180) (+/-30 days)	Month 12 (Day 365) (+/-2 weeks) *Phone Call Follow-up

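### Section 8.2.4 permits further infusions after some stopped infusions for which Appendix 1 bars them, and nothing says which text prevails

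*Combined protocol and SAP*

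**What the plan says.** Two lists deal with what follows a stopped infusion.

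Section 8.2.4, item 2: "Any subject whose infusion is stopped due to cardiorespiratory distress will not receive further IP infusions until it is considered safe" in the Investigator's opinion. It then adds: "A subject may still be able to receive additional infusions", subject to the Investigator's judgement. Item 1, on cardiorespiratory signs persisting more than 3 hours after the infusion ends (its examples include shortness of breath, tachycardia, hypotension and palpitations), closes with the same permission.

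Appendix 1 has its own block titled "Subject Stopping Guidelines". Item 2 reads: "Any subject whose infusion is stopped due to cardiorespiratory distress will receive no further IP infusions but will continue with all scheduled follow-up". Item 3 covers a subject with any sign or symptom that, at the Investigator's discretion, "warrants the discontinuation of infusion will receive no further IP infusions". In both items the Investigator's opinion on safety qualifies only whether follow-up continues, not the bar itself. Appendix 1 items 1 and 4 do not address re-infusion.

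Each addendum cites both sources. Under Infusion Monitoring Guidelines (A.10, B.9, C.10, D.10): "Refer to section 6.4.1 and Appendix 1 of the main protocol". Under Stopping Guidelines (A.12, B.11, C.12, D.12): "Refer to section 8.2.4 of the main study protocol for further stopping guidelines".

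**The concern.** The trigger in the two item 2 texts is the same, but the consequence differs: a hold that the Investigator may lift in one place, an unqualified bar in the other. The situation is foreseen. Sections 6.4.1 and 8.2.1 set oxygen-saturation conditions under which an infusion is stopped, and Addenda A, C and D offer later infusions.

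A site that re-infuses under Section 8.2.4 would be departing from Appendix 1. A monitor or the DSMB could not tell from the protocol whether that is a deviation. Safety of repeat infusion is the primary objective of Addenda A and C, so the rule also bears on who may contribute data to that question. The documents do not show that any endpoint or monitoring boundary is affected.

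**Working it through.** No figure in the plan sizes this, so the check compares the texts.

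**1. Trigger and consequence**

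| Reason | Section 8.2.4 | Appendix 1 |
|---|---|---|
| Infusion stopped for cardiorespiratory distress | Item 2: held until judged safe; later infusions possible | Item 2: no further IP infusions |
| Persistent cardiorespiratory sign that also led to discontinuation | Item 1: later infusions possible | Item 3: no further IP infusions |
| Other sign or symptom leading to discontinuation | No matching item | Item 3: no further IP infusions |

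The first two rows conflict. The third is a gap in Section 8.2.4, not a contradiction.

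**2. Is one text ranked above the other?**

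- Section 8.2.5 has discontinuation in its title, but its body says only that the Appendix 1 guidelines "list the study requirements for subject observation and discharge after IP administration". It does not rank them against Section 8.2.4.
- The closing paragraph of Section 8.2.4 says its guidelines are not formal stopping rules. That concerns closure of enrollment, not re-infusion of one subject.
- Sections 6.4.1 and 8.2.1 say when to stop an infusion and are silent on re-infusion.
- The addenda invoke both sources. A.1 and C.1 also carry over earlier procedures unless otherwise noted, without ranking sections.

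No precedence statement was found. Pages removed from the public copy could not be checked.

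**3. When do the texts part?**

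- Subject not re-infused: neither text is breached, because Section 8.2.4 permits and does not require.
- Subject judged unsafe: no re-infusion under Appendix 1 or Section 8.2.4 item 2. Addenda A, C and D also exclude on the investigator's safety opinion (item 6 of A.4.2, C.4.2 and D.4.2).
- Subject judged safe and re-infused: allowed by Section 8.2.4, barred by Appendix 1. This is the only point of conflict.

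**4. Where can that arise?**

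- Not within the first pilot infusion (Section 6.2), the randomized phase (Section 3.2) or Addendum B (B.4), each of which gives one infusion.
- Addenda A and C: yes. C.1 reports that 12 subjects had already received two doses, so what remains is mainly Addendum C.
- Addendum D after a stopped placebo infusion: arguable. Section 6.1 defines the investigational product as hMSCs, so a first hMSC dose may not be a further IP infusion. Against that, Appendix 1 calls the blinded bag IP, and D.1 counts the placebo as one of the subject's two infusions.

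**5. Outer bound on optional later infusions**

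Pilot 15 × 3 = 45; Addendum B subjects 20 × 3 = 60; Addendum D 10 × 1 = 10. The total is 45 + 60 + 10 = 115 if every option is taken up. At least 12 (the second pilot doses) had been given: 115 − 12 = 103. This counts planned opportunities, not affected subjects; only infusions that follow a stopped one matter, and their number is not given.

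**The case against.** The strongest reply is that the protocol already signposts an answer: under Stopping Guidelines every addendum cites only Section 8.2.4, and Appendix 1 is cited only for infusion monitoring. That lean is real. It does not settle the matter, because Section 8.2.4 is cited for *further* guidelines, which adds to Appendix 1 without displacing it, and because Appendix 1 contains its own stopping block.

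A second reply is that a site can satisfy both texts by never re-infusing. This is correct. A reader might infer from the two item 2 texts that a site cannot comply with both; the documents do not support that, since Section 8.2.4 never requires a re-infusion. What remains is that its express permission cannot be used without breaching Appendix 1.

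A third reply is that few or no subjects are affected. C.1 reports that the 12 subjects with two doses had no adverse effects attributed to the study agent, and C.2 reports no adverse effects. Neither statement shows that no infusion was stopped, but both point to low reach.

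**Conclusion.** The contradiction holds: Section 8.2.4 items 1 and 2 permit re-infusion in circumstances where Appendix 1 items 2 and 3 bar it, and no precedence is stated. It is a conflict between a permission and a prohibition, live only if the permission is used.

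Its size cannot be estimated. The number of affected subjects is unknown and may be zero. Two inferences should be resisted. The 115 possible later infusions are not a measure of exposure to this conflict. Nor does the plan allow re-infusion of a subject the Investigator considers unsafe, since the addenda's own exclusions apply. The Addendum D branch depends on whether placebo counts as investigational product, which the documents leave open.

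Given the narrow reach and the absence of any shown effect on an analysis, this is a should-fix item. It merits correction because it concerns a subject-level safety instruction.

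**What to change.** Reconcile Section 8.2.4 items 1 and 2 with Appendix 1 items 2 and 3, so that one rule on re-infusion after a stopped infusion is stated once. State whether the rule covers stops for signs or symptoms other than cardiorespiratory ones, and whether a stopped placebo infusion counts for Addendum D. Have the other location, and A.10/A.12, B.9/B.11, C.10/C.12 and D.10/D.12, refer to that single statement. Which rule to adopt is a clinical decision on which no position is taken here.

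The cost is wording in two places plus cross-references in the addenda, with no change to sample size, schedule or analysis.

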APPENDIX 2: Dobutamine Stress Echocardiogram (DSE) Guidelines

A Dobutamine Stress Echocardiogram (DSE) will be performed at screening and at the Month 6 follow-up visit. Dobutamine is a chemical, which can assist in mimicking the effect of exercise on subjects in order to assess the heart muscle and ejection fraction when under stress.

Procedure Details:

1. Obtain baseline heart rate, blood pressure, Electrocardiogram (ECG), physical exam, and echocardiographic images on the study participant.
2. Place an Intravenous (IV) line to administer Dobutamine.
3. Administer progressively increasing doses of Dobutamine (5, 10, 20, and 30 mcg/kg/min) in 3-minute intervals.
4. Obtain Heart rate, Blood Pressure, ECG, and echocardiographic images at each dosage.
5. After completing measurements at 30mcg/kg/min dosage, discontinue Dobutamine and allow heart rate to recover to baseline and obtain repeat echocardiographic images.

Required Data Points:

6. Right Ventricular end-diastolic dimension (RVDd)
7. Interventricular Septal end-diastolic dimension (IVSd)
8. Left Ventricular Internal end-diastolic dimension (LVIDd)
9. Left Ventricular Internal end-systolic dimension (LVIDs)
10. Left Ventricular Posterior Wall end-diastolic dimension (LVPWd)
11. End-Diastolic Volume (EDV)
12. End-Systolic Volume (ESV)
13. Left Atrial (LA) dimension
14. Peak infusion rate
15. Peak heart rate
16. Peak blood pressure (systolic/diastolic)
17. Resting biplane ejection fraction
 - Ejection fraction at 5 mcg/kg/min
 - Ejection fraction at 10 mcg/kg/min
 - Ejection fraction at 20 mcg/kg/min
 - Ejection fraction at 30 mcg/kg/min
18. Evidence of Mitral Valve Regurgitation (MR)
19. Evidence of Pericardial Effusion (PE)

Addendum A: Pilot Subjects Optional Follow-on Phase

A.1 Rationale and Description of second infusion for first 15 subjects on pilot phase

This addendum protocol is designed to test the safety of a second infusion of allogeneic mesenchymal stem cells 12 to 18 months following a first infusion.

Subjects in the pilot phase that received one (1) infusion of allogeneic MSCs are eligible to participate in this optional follow-on phase for a second dose. Because several studies, reviewed below, have now shown safety of repeat doses of MSCs in a variety of medical conditions, additional safety testing in the subject population of aging frailty enrolled in the CRATUS trial is required⁹². All study specific processes and procedures included in the pilot phase of the protocol apply in this addendum unless otherwise noted.

A.2 Demonstrated Safety and Increased Efficacy of Multiple Infusions of Allogeneic Mesenchymal Stem Cells

Active clinical trials and ongoing preclinical work provide an accumulating data set supporting the safety and, in some cases, therapeutic efficacy of allogeneic mesenchymal stem cells (MSCs). Allogeneic mesenchymal stem cells are both immunoprivileged and immunosuppressive, thereby enabling their use as an allograft⁹³. Cellular therapy with allogeneic MSCs has abundant support from both animal studies and human clinical trials for a wide range of disorders (Table 1). For example, the POSEIDON study addressed the major issue of the use of allogeneic MSCs as a cell-based therapeutic¹⁸. In this study, subjects with cardiac failure were randomized to receive either autologous MSCs or identically prepared allogeneic MSCs from healthy donors.

Accumulating evidence also supports the concept that repeated doses and/or co-administration of allogeneic MSCs could further enhance therapeutic outcomes. This is an extremely important area for medical investigation, since repeat dosing could potentially have an additive effect and/or reverse disease pathology, depending on the disorder.

Recently, several clinical studies have demonstrated that multiple infusions of allogeneic MSCs are well tolerated with minimal side-effects. Importantly, repeat dosing has no increased level of side effects compared with single doses. For example, results from Franco Locatelli's group⁹² clearly demonstrate the safety and efficacy of multiple allogeneic MSC infusions in children with steroid-refractory acute graft versus host disease (aGvHD). Doses in these studies were $1-2 \times 10^6$ MSCs/kg recipient body mass, and each child received on average 2 doses (range was 1-13 doses) separated on average by 15 days (range 3-43 days). The results of this study indicated increased effectiveness when the therapy was commenced early in the disease. Furthermore, the study indicated the therapeutic benefits of repeat doses to subjects who did not achieve complete remission after a single dose.

Koc et al⁹⁴; further investigated Hurler syndrome (mucopolysaccharidosis type-IH) and metachromatic leukodystrophy (MLD) and studied allogeneic MSCs based on their potential to differentiate into cells of bone, cartilage, tendon, muscle and other adventitial tissues and offer potential for corrective cellular therapy⁹⁵. Their results demonstrated no infusion-related toxicity, improvement in nerve conduction, and bone mineral density was either maintained or improved in all subjects.

A Phase II study on the 3-year efficacy of allogeneic MSCs in the treatment of system lupus erythematosus (SLE) was reported by Lingyun Sun's group⁹⁶. The results of this study demonstrated the therapeutic efficacy of allogeneic MSCs in treating SLE. However, no advantage was found by administering a second or higher dose of allogeneic MSCs. Despite this lack of additional efficacy over a single dose, the results of this study confirmed the safety of multiple infusions of allogeneic MSCs. The doses (1×10^6 MSCs/kg body mass) were administered 1 week apart. Another study reported on the use of repeated dosing of allogeneic MSCs in subjects with chronic obstructive pulmonary disease. The study showed minimal therapeutic efficacy after 2 years¹⁹. Importantly, in this subject population repeated allogeneic MSC infusions, which were given 4 times at 30 day intervals (1×10^8 MSCs/infusion) were safe.

Taken together, these various clinical studies provide a solid rationale for repeat allogeneic MSC infusions. In no case did the administration of multiple doses lead to a significant increase in the frequency of adverse effects, or to a decrease in therapeutic efficacy over a single dose. In many cases, repeated infusions indeed improved clinical outcomes, demonstrating an additive effect of allogeneic MSC therapy. Given these promising results, investigations are now warranted to determine optimal dosing frequency and total doses of allogeneic MSCs to administer.

It is particularly important to establish safety of repeat doses of allogeneic MSCs in the subject population enrolled in the CRATUS study. These individuals are of older age and are not represented in the previous studies described. In this follow-on study subject s in an earlier open label pilot study will be asked to participate in this repeat dosing protocol.

A.3 STUDY OBJECTIVES AND ENDPOINTS

A.3.1 Study Objectives

A.3.1.1 Primary Objective

1. Demonstrate the safety and tolerability of a second intravenous infusion of allo-hMSCs in subjects with aging frailty who had previously received an infusion of allogeneic MSCs as part of the pilot phase of the protocol.

A.3.1.2 Secondary Objectives

1. To explore treatment efficacy (decrease in frailty, frequency of acute exacerbations, change in symptom related quality of life, improved cardiovascular status, decrease in inflammatory biomarkers, endothelial function and 1 year survival).

A.3.2 Study Endpoints

A.3.2.1 Primary Endpoints (Safety)

1. Safety (Primary): Incidence (at one-month post second infusion) of any treatment-emergent serious adverse events (TE-SAEs), defined as the composite of: death, non-fatal pulmonary embolism, stroke, hospitalization for worsening dyspnea and clinically significant laboratory test abnormalities, determined per the Investigator's judgment.

Laboratory tests included in the primary endpoint include the following:

- Serum chemistry: chloride, sodium, Carbon Dioxide, BUN, creatinine, glucose, calcium, AST/SGOT, ALT/SGPT, total bilirubin (fractionate if total >1.5 times normal), alkaline phosphatase, albumin,
- Hematology (CBC): hemoglobin, hematocrit, platelets, WBC, WBC differential

A.3.2.2 Secondary Endpoints (Efficacy)

The following efficacy endpoints will be evaluated in this trial (During the screening, baseline, Month 3 and/or Month 6 visits):

1. Difference in rate of decline of Frailty defined as:
 - Reduced Activity (assessed via CHAMPS questionnaire)
 - Slowing of Mobility (assessed via a 4 meter gait speed test and SPPB assessment)
 - Weight Loss
 - Diminished handgrip strength (assessed via dynamometer)
 - Exhaustion (assessed via the MFI questionnaire)
 - Decrease in subject quality of life assessment(s) (assessed via ICECAP, SF-36, EQ-5D Questionnaires)
2. Death from any cause.
3. Change between screening and 6 months in dobutamine stress echo induced ejection fraction.
4. Change between screening and 6 months for the following panel of inflammatory markers: CRP, IL-6, D-dimer, fibrinogen, CBC with differential, and TNF α .

5. The incidence of each component of the primary endpoint including non-fatal pulmonary embolism, stroke, hospitalization for worsening dyspnea and clinically significant laboratory test abnormalities
6. Change in Smell Identification Test (UPSIT)

A.4 Inclusion and Exclusion Criteria

A.4.1 Inclusion Criteria for Follow-on Phase

In order to participate in this study, a subject MUST:

1. Provide written informed consent.
2. Subjects age ≥ 60 and ≤ 95 years at the time of signing the Informed Consent Form for the second infusion.
3. Have previously participated in the pilot phase of this trial
4. Female subjects must have an FSH ≥ 25.8 mIU/mL, if not currently on hormone replacement therapy.

A.4.2 Exclusion Criteria for Follow-on Phase

In order to participate in this study, a subject MUST NOT have any of the following:

1. Score of ≤ 24 on the Mini Mental State Examination (MMSE)
2. Inability to perform any of the assessments required for endpoint analysis (report safety or tolerability concerns, perform PFTs, undergo blood draws, read and respond to questionnaires).
3. Active listing (or expected future listing) for transplant of any organ.

4. Clinically important abnormal screening laboratory values, including but not limited to: hemoglobin <8 g/dl, white blood cell count <3000/mm³, platelets<80,000/mm³, INR > 1.5 not due to a reversible cause (i.e. Coumadin), aspartate transaminase, alanine transaminase, or alkaline phosphatase > 3 times upper limit of normal, total bilirubin > 1.5 mg/dl.
5. Serious comorbid illness that, in the opinion of the investigator, may compromise the safety or compliance of the subject or preclude successful completion of the study. Including, but not limited to: HIV, advanced liver or renal failure, class III/IV congestive heart failure, myocardial infarction, unstable angina, or cardiac revascularization within the last six months, or severe obstructive ventilatory defect.
6. Any other condition that, in the opinion of the investigator, may compromise the safety or compliance of the subject or preclude successful completion of the study.
7. Be an organ transplant recipient.
8. Have a clinical history of malignancy within 3 years (i.e., subjects with prior malignancy must be disease free for 3 years), except curatively-treated basal cell carcinoma, squamous cell carcinoma, melanoma in situ or cervical carcinoma if recurrence occurs.
9. Have a non-pulmonary condition that limits lifespan to < 1 year.
10. Have a history of drug or alcohol abuse within the past 24 months.
11. Be serum positive for HIV, hepatitis BsAg or Viremic hepatitis C.
12. Be currently participating (or participated within the previous 30 days) in an investigational therapeutic or device trial. This does not exclude subjects that participated in the pilot phase.
13. Be a female who is pregnant, nursing, or of childbearing potential while not practicing effective contraceptive methods. Female subjects must undergo a blood or urine pregnancy test at screening and within 36 hours prior to infusion.
14. Have hypersensitivity to dimethyl sulfoxide (DMSO)

A.5 Dosing

After subjects complete their Month 12 follow-up phone call visit in the pilot phase (first infusion), all 15 subjects will then have the option of receiving additional infusions of allogeneic hMSCs: 1×10^8 (100 million) cells delivered via peripheral intravenous infusion.

The Allo-hMSCs will be derived from donors meeting criteria for allogeneic unrelated human bone marrow stem cell source manufactured by the University of Miami.

A.6 Dosage Rationale

A safety profile for IV infusion of hMSCs was based on results from previous completed toxicology results (Hare et al. 2277-86). The results from previous studies demonstrate that the product can be administered intravenously without toxic events at up to 65 x 10^6 hMSC/kg dose delivered in one bolus infusion or at 100 x 10^6 hMSC/kg cumulative dose delivered by 5 infusions (20 x 10^6 hMSC/kg per infusion).

The evidence supports the conclusion that it is feasible to dose subjects in this study based on a standard dose of hMSCs rather than per kilogram of body weight. The total cell number corresponds to a range of 1.3 - 4.4 x 10^6 hMSCs per kg per infusion for subjects with 45 to 150kg body weight, the weight range for this study.

Therefore, results from previous trials support the rationale on the safety and potential efficacy of a second infusion of the selected maximum dose of 100 x 10^6 allo-hMSCs.

A.7 Administration Rate

Prior clinical trials have used rates up to 30x 10^6 hMSC/min where no infusion related toxicity was observed.

In the proposed study addendum, the cell dose to be delivered is 1 x 10^8 (100 million), in the following total volume:

- 40ml for 100 million dose (5 million hMSC/min)

Cells are placed in an 80ml bag and will be delivered at a rate of 2ml/min, and delivered at a maximum rate of 16x 10^6 hMSC/minute and will last approximately:

- 40 minutes for delivery of 40ml of 100 million dose in an 80 ml bag

A.8 Data and Safety Monitoring Board (DSMB)

DSMB will continue to provide the same oversight as noted in Section 9.4 of the Main protocol.

A.9 Concomitant Treatments, Procedures, and Nondrug Therapies

Refer to section 4.3 of the main study protocol

A.10 Infusion Monitoring Guidelines

Refer to section 6.4.1 and Appendix 1 of the main protocol.

A.11 Adverse Events and Serious Adverse Events

Refer to section 8.9 through 8.15 of the main study protocol.

A.12 Stopping Guidelines

Refer to section 8.2.4 of the main study protocol for further stopping guidelines.

A.13 Payments to Subjects and Donors in the Follow-on Phase

Subjects will be reimbursed \$25 at the end of each follow-up visit (Month 1 – Month 6 for a total remuneration of \$75. These disbursements are meant to cover the time required to complete these study visits and all necessary travel and parking expenses.

Normal donors for generation of allo-MSC will be reimbursed \$500 at the end of BM aspiration. This payment will compensate donors for lost time, parking, and travel expenses.

A.14 Study Procedures for Pilot Phase Optional Second Infusion

Table A1: Time and Events Table for Optional Pilot Phase Second Infusion Schedule

Visit Schedule for Second Infusion	Screening ± 6 Months	Baseline (-4 weeks)	Day 1	Month 1 (Day 30) (+/- 2 weeks)	Month 3 (Day 90) (+/- 30 days)	Month 6 (Day 180) (+/-30 days)	Month 12 (Day 365) (+/-2 weeks) *Phone Call Follow-up
Informed Consent	x						
Full Medical History	x						
Physical Exam	x	x	x	x	x	x	
12-lead (ECG)	x	x	x	x	x	x	
Concomitant Medications	x	x	x	x	x	x	x
Mini Mental State Examination (MMSE)	x					x	
Infusion Treatment (IP)			x				
Dobutamine Stress Echo Test (DSE)	x					x	
Bone Density Scan (DEXA) ⁸		x				x	
FEV-1		x				x	
6 Minute Walk Test		x				x	
4 Meter Gait Speed Test ⁷		x				x	
SPPB Assessment		x				x	
Dynamometer (handgrip) ⁹		x				x	
Smell Identification Test (UPSIT)		x				x	
IIEF, SQOL-F Questionnaires		x		x	x	x	
QOL Questionnaires (ICECAP, EQ-5D, SF-36,CHAMPS, MFI)		x		x	x	x	
Urinalysis	x			x	x	x	
Hemat., Chem., CBC, LFTs, INR, and other labs ¹	x		x	x	x	x	
HIV 1, HIV 2, Hep. B & C, and CMV	x						
Serum or Urine Pregnancy Test ²	x		x				
Review Adverse Events			x	x	x	x	x
Immune Monitoring ⁴			x	x	x	x	
Biomarker Assessment ³			x			x	
Optional: Brachial Ultrasound ⁵		x			x		
Optional: Endothelial blood samples ⁶		x			x		

Time and Events Table Key:

1 – The minimal laboratory requirements for hematological, liver function and renal function include:

Hematology Tests: white blood cell count, platelet count, hemoglobin and hematocrit, red blood cell count, CBC with Differential: neutrophils, lymphocytes, monocytes, eosinophils, and basophils.

Liver Function Tests: Albumin, alkaline phosphatase, alanine transaminase, aspartate aminotransferase, prothrombin time / activated partial thromboplastin time, and bilirubin(fractionate if total >1.5 times normal).

Renal Function Tests: creatinine, creatinine clearance, blood urea nitrogen (BUN), glomerular filtration rate, sodium, potassium, chloride, calcium, carbon dioxide, total protein, glomerular filtration rate (GFR), and glucose, (HbA1c) will be collected at every follow-up visit only for subjects diagnosed with diabetes mellitus (DM).

Serum Uric Acid, Pro-BNP, and high sensitivity C-reactive protein (hs-CRP), IL6, fibrinogen, D-Dimer, DNA, TNF α , testosterone (males only) and estrogen (females only).**

- Laboratory work may be completed at a diagnostic center or home health agency should the subject be unable to come to the site.

*** Deoxyribonucleic acid (DNA) will only be collected once during the subject's participation. There is no specific point DNA needs to be collected as it can occur at any time point.*

2 – A serum or urine pregnancy test will be completed within 36 hours prior to infusion for females of childbearing potential.

3 – The following biomarkers will be analyzed (Approximately 10mL blood samples will be collected):

- **Cell-surface markers:** CD19, CD27, IgD, and CD5 (for Switched Memory, Naïve, Late/Exhausted, IgM memory B cells and regulatory B cells); CD19 and intracellular TNF- α (to assess intracellular TNF- α); CD3, CD4, CD8, CCR7 and CD45RA (for Central Memory, Naïve, Effector Memory, TEMRA T cells and CD4 to CD8 ratio); CD3, CD25 and FOXP3 (to assess regulatory T cells)
- **Transcriptomic/Proteome:** RNA, miRNA, protein samples, and telomerase, akt
- **Growth factors:** Sdf-1, notch,
- **Functional Assays:** cell growth rate, VEGF, and CFU assay

4 – Immune monitoring for graft rejection. Calculated panel reactive antibodies (cPRA) will be performed on day 1 and 6 months post treatment to assess for donor specific antibodies. In addition, the following markers will be used for analysis to assess for activated T-cells based upon a CD3⁺CD25⁺ (late/chronic T cell activation) or CD3⁺CD69⁺ phenotype (early T cell activation).

5 – Optional brachial ultrasound to assess endothelial function.

6 – Optional: An additional five (5) lavender top tubes (EDTA) will be drawn of approximately 8ml per tube.

7 – 4 meter gait speed test will be performed twice per visit and the average of the exams will be taken.

8 – DEXA scan will be performed at baseline and Month 6. The scans of the hip and spine for bone density, and total body composition will be assessed at both visits.

9 – Dynamometer will be performed at least three (3) times during each applicable visit for each hand. The three values collected will be averaged for each hand. (Please reference the instruction manual on how to administer.)

10– Infectious disease tests – HIV, HIV 2, Hep B (HBsAG, Anti-HBs, Anti-HBc), and Hep C (Anti-HCV), VDRL, Syphilis, West Nile Virus, and CMV. (Conducted within 30 days of infusion, if test expire prior infusion, they must be performed again)

A.15 Study Visits

A.15.1 Screening Visit for second infusion

See Table A1 for the procedures and assessments to be performed during the screening visit of the study for the 15 pilot subjects that consent to participate in a second infusion. All screening visit test and procedures will occur upon signing the informed consent form (ICF). No screening exams will take place until the subject is fully informed of the research and signs the consent form. The tests may take place over several days and will need to be completed prior to the start of the baseline visit. There will be up to a 6 month window from the subjects Month 12 follow-up visit to the subject's additional infusion.

A.15.2 Baseline Visit for second infusion

See Table A1 for the procedures and assessment to be performed during the baseline visit of the study. Once all screening exams are completed and it has been determined that the subject remains eligible for the study, subjects will be enrolled into the study. The baseline visit will take place within four weeks of the infusion. The listed procedures should all be performed as soon as practicable.

Endothelial function (Optional Assessments) will occur upon the subject signing the optional section of the informed consent form (ICF). No endothelial function tests will take

place until the subject is fully informed of the research and signs the optional portion of the consent form.

- Brachial ultrasound testing and blood collection will be performed to assess endothelial function in the aging frailty population at baseline and 3 months post stem cell infusion. This will help provide cumulative data in assessing whether or not stem cell infusion improves endothelial function.
- Flow Mediated Diameter percent change (FMD%): All measurements of the brachial artery diameter and FMD will be performed in the morning, in a quiet and dark room and at controlled ambient temperatures between 20°C and 26°C. Studies will be conducted after an overnight fast of at least 10 hours (water is permitted), with the subjects supine and after 10 minutes of rest. The subject's right arm will be comfortably immobilized in an extending position, allowing for ultrasound scanning of the brachial artery 5–10 cm above the antecubital fossa. In each examination, recording of vessel images will be followed by inflation of a cuff to supra-systolic pressure (40 to 50 mmHg above systolic pressure) for 5 minutes. Then the cuff will be deflated and the brachial artery diameter will be imaged and recorded for 3 minutes. FMD% more than 10% is considered a normal response. Lower than 10% FMD% reflects endothelial dysfunction, which means a high likelihood to develop cardiovascular event in the future. Subjects with negative FMD% results (the artery is constricted after stress and not dilated as was expected) have the worst prognosis.
- Blood drawn from fasting subjects will be separated and the serum will be frozen until processed as one batch towards the end of the study. Blood will be processed twice – in the beginning of the study and after 3 months.
- Biochemical analysis: soluble pro inflammatory cytokines (interleukin-1, interleukin-6, interleukin-10, VEGFR2, TNF-a).
